### **I. BACKGROUND AND SIGNIFICANCE**

Each year, 11,000 people suffer a spinal cord injury (SCI) in the U.S. In the first year after an SCI, there are profound declines in function, forming an underlying substrate for future cardiovascular morbidity and mortality. In fact, acquired cardiovascular disease (CVD) is an increasingly recognized consequence of SCI and is the leading cause of death in this population. Almost all risk factors are amplified in those with SCI; though incompletely understood, the almost 10-fold prevalence of CVD results at least in part from profound physiologic >detraining= resulting from motor impairment and immobility. Moreover, physical rehabilitation after SCI needs to move beyond the goal of maximizing independence to focus on maintenance of optimum health and fitness; vigorous exercise of the paralyzed limbs may help achieve these objectives as well as reduce cardiovascular risk. However, effective interventions preventing acute declines that lead to cardiovascular compromise and increased risk in SCI are lacking.

An appropriate exercise intervention early after injury could prevent or lessen many of the acute declines that predispose those with SCI to a myriad of long-term health risks. However, exercise therapy for those with SCI is challenging and when employed, is typically limited to upper body activity. Recently, we developed a unique form of exercise for those with SCI that specifically mirrors exercise performed by those without SCI. Functional Electrical Stimulation Row Training (FES-RT) couples volitional arm and electrically controlled leg exercise. In contrast to other forms of exercise (arms only exercise, FES leg cycling, or FES leg cycling with arm exercise), FES-RT is unique in that the non-innervated legs are integral for the performance of this whole body exercise. The full rowing stroke is produced by both the (stimulated) legs and arms, increasing the active muscle mass and resulting in a hemodynamic profile that produces the beneficial cardiac loading conditions of large muscle mass exercise. As such, FES-RT may be a safe and effective way to attenuate cardiovascular declines following SCI. Our preliminary work in chronic SCI has demonstrated the feasibility of FES-RT and suggests important attendant changes in cardiovascular health. However, it is imperative that the positive impact of FES-RT be determined in those with acute SCI, because it is at the early stages of injury that future medical complications can be prevented. We will also study those with chronic SCI to provide a comparison of the magnitude of adaptations across a range of injury duration.

# PARTNERS HUMAN RESEARCH COMMITTEE

## DETAILED PROTOCOL

### II. SPECIFIC AIMS

- 1) *To document changes in body composition (visceral adiposity) and insulin sensitivity (homeostatic model assessment) resulting from FES-RT in comparison to a time (wait-list) control and to arms-only row training (arms-only-RT)*

We hypothesize FES-RT will mitigate against increased visceral adiposity and reduced insulin sensitivity occurring with acute SCI and that FES-RT will be more effective than arms-only-RT.

- 2) *To quantify changes in key indices of cardiovascular health (serum lipids) and control (arterial baroreflex gain) with FES-RT in comparison to a time control and to arms-only-RT*

We hypothesize FES-RT will prevent the worsening lipid profile and compromised baroreflex function occurring with acute SCI and that FES-RT will be more effective than arms-only-RT.

- 3) *To characterize changes in myocardial structure (left ventricular wall thickness) and function (left ventricular diastolic velocity) with FES-RT in comparison to a time control and to arms-only-RT*

We hypothesize FES-RT will counter the ventricular wall thickening and declining ventricular function occurring with acute SCI and that FES-RT will be more effective than arms-only-RT.

- 4) *To compare the body composition, insulin sensitivity, cardiovascular health and control, and myocardial structure and function and the magnitude of adaptations to FES-RT across a range of injury duration from acute to chronic SCI.*

We hypothesize that cross-sectional declines in all variables will relate directly to injury duration and that therefore the magnitude of adaptations will be greater with longer injury duration.

### III. SUBJECT SELECTION

We will enroll 60 individuals within twelve months post SCI to obtain data on 50 individuals. One-half of the subjects (N=25) will be randomized to immediately enroll in 6 months of FES-RT. One third (N=18) will be randomized to a wait-list to provide time control data from baseline to 6 months. A wait-list control group is routine in exercise studies because most volunteers are interested in participating in an exercise program. Hence, time controls are difficult to capture since many of those randomized to receive

## PARTNERS HUMAN RESEARCH COMMITTEE

### DETAILED PROTOCOL

no exercise either drop from the study entirely, or end up pursuing some form of exercise on their own. Therefore, a vehicle for enrollment of a time control group that is acceptable to most volunteers is a wait-list. A six month time control will provide data on expected declines. One-third (N=17) of subjects will be randomized to six months of arms-only-RT. This will provide data on a comparator that represents a form of arms-only exercise that would be available to those with SCI. These subjects will undergo six months of FES-RT after completing arms-only-RT. This will enhance subject retention and provide data for secondary analysis.

To enhance subject recruitment we may enroll subjects into the study before they are 3-months post injury, most likely while they are still in-patients at Spaulding Rehabilitation Hospital. This will help subjects to schedule and plan for transportation for study assessments and training to begin when they reach 3-months post injury. No study assessments will be scheduled before 3-months from time of their SCI. Study participation will not interfere with scheduling of any normal inpatient therapy, nor will study participation take place during normal therapy. In-patients will need to be cleared to participate by their treating physician.

In addition we will enroll another 25 individuals with chronic SCI to serve as a comparator to the acute FES-RT group. Neither a wait-list nor arms-only-RT are required for this population. Time control data from baseline to 6 months are not needed since expected declines would be minimal over this time period after the acute phase of injury. In addition, the fourth aim is solely focused on responses to FES-RT and so a comparator that represents a form of arms-only exercise available to those with SCI is not necessary. Subjects in the chronic group will be at least 1 year post spinal cord injury with adult onset of SCI(SCI occurrence after 18 years of age).

All volunteers will continue with regular physical rehabilitation except for modalities that overlap study interventions (e.g., FES-cycling).

All Subjects will be 18-40 years of age with spinal cord injury (American Spinal Injury Association A, B, C) at the neurological level of C5-T12. Subjects will be medically stable (no treatment for DVT, no orthostasis, no spinal precautions or weight-bearing precautions associated with a healing long-bone fracture) and be able to tolerate the stimulation without dysreflexia. Dysreflexia in some participants is expected in the initial FES sessions, but only those in whom dysreflexia abates with repeat exposures will be included.

## PARTNERS HUMAN RESEARCH COMMITTEE

### DETAILED PROTOCOL

Participants will be excluded if they have: 1)Hypertension (blood pressure >140/90 mmHg), 2) significant arrhythmias, 3) coronary disease, 4) diabetes, 5) renal disease, 6) cancer, 7) epilepsy, 8) current use of cardioactive or antidepressant medications, 9) family history of significant arrhythmia or sudden cardiac death 10) orthostatic hypertension with symptomatic fall in blood pressure > 30 mmHg when upright 11) current grade 2 or greater pressure ulcers at relevant contact sites, 12) other neurological disease, 13) peripheral nerve compressions or rotator cuff tears that limit the ability to row, 14) history of bleeding disorder, 15) regular use of tobacco, 16) current deep venous thrombosis, 17) severe spasticity (that prevent rowing movements), 18) severe autonomic dysreflexia, 19) implanted electronic cardiac device (pace maker, cardiac defibrillator), 20) ventilator-dependent condition, 21) sensations that prevent the use of the electrical stimulation, 22) other medical contraindications to vigorous exercise.

The American College of Sports Medicine's Guidelines for Exercise Testing and Prescription 9th edition will be followed as the standard of care along with the clinical specialists' opinion (Drs. [name] and [name]) regarding any additional pre-participation screening needed prior to beginning this vigorous exercise training program.

Pregnant and nursing women are not eligible for this study because of the potential risk to the fetus from radiation that goes along with the DXA scan. Women who are able to become pregnant must agree to use contraceptive methods while participating in the study. Acceptable contraceptive methods are: a) hormonal methods (birth control pills, patches, injections, vaginal ring or implants); b) barrier methods (condom or diaphragm, with a foam, cream or gel spermicide); c) intrauterine device (IUD); or d) abstinence (no sex). Women are considered unable to become pregnant if they are menopausal and have not had a menstrual period for at least one year or if they have had a hysterectomy (surgical removal of your uterus and/or ovaries).

#### **IV. SUBJECT ENROLLMENT**

Research study staff will obtain volunteer consent in accordance with guidelines established by the Institutional Review Board during the first visit to the Laboratory. Participants will be sent the consent form at least 48 hours in advance so they have ample time to read and ask questions. Participants are encouraged to ask questions and are reminded that participation is strictly voluntary and will not affect their current or future care at Spaulding Rehabilitation Hospital or any of its affiliates.

## PARTNERS HUMAN RESEARCH COMMITTEE

### DETAILED PROTOCOL

#### **V. STUDY PROCEDURES**

Volunteers who enroll in the study before 3-months from their injury date will have a partial screening visit in which informed consent and detailed health history will be obtained(all other assessments will be scheduled after they reach at least 3-month post SCI. Once recruited for the study volunteers (that are at least 3-months post injury) will visit the laboratory for a health screening session to further determine eligibility. This two may require one or two visits depending on the ability to schedule with the physician. It will include obtaining informed consent, detailed health history, PROMIS 57 questionnaire, a standard physical exam (ASIA exam and Ashworth Scale) performed by a physician (if necessary), height and weight measurements, resting blood pressure, electrocardiogram (EKG) and FES-device test.

Note: If an ASIA exam and Ashworth Scale have previously been performed by a physician and results can be obtained, those medical records may be used and the physical exam will not be necessary during screening.

Subjects may also be asked to provide additional medical records or may need further testing to determine their eligibility and the safety of their participation in this program which includes regular vigorous exercise. These additional tests may or may not be covered by insurance. The subject will be responsible for obtaining any additional testing and providing the program with medical records or results.

Approximately 40% of spinal cord injured women have amenorrhea for an average of eight months. Therefore, menstrual status will be tracked and explored as a potential covariate. A prospective menstrual diary will be collected for three months prior to each data acquisition time-point. For each monthly diary, women will mark the day of the month when bleeding occurred and rate the heaviness of blood flow (spotting to heavy). If no bleeding occurred during a particular month or the menstrual period, this will be indicated. Bleeding patterns will be used to define normal, irregular, or absent menstrual cycles.

# PARTNERS HUMAN RESEARCH COMMITTEE

## DETAILED PROTOCOL

### Training Protocols for Each Study Group

#### **1) FES-RT GROUP (Acute and Chronic SCI)**

##### FES-strength training prior to FES-RT

To be able to FES-row, a certain level of leg muscle strength and endurance is essential; therefore, prior to FES-row training, the ability of the subject to perform 30 minutes of FES-induced leg extension will be evaluated. Electrodes will be placed over the motor points of the rectus femoris, vastus medialis, vastus lateralis, biceps femoris and semitendinosos . A four-channel Odstock stimulator will alternate stimulation between the hamstrings and the quadriceps while the subject is seated in their wheelchair or on an exam table. The stimulus parameters will be set at 12 second periods with a 6 second on-time per channel without a ramp and with a pulse width of 450ms at 50 Hz. The intensity of the stimulus to the quadriceps will be set at the level that produces full knee extension. If the knee does not achieve full extension due to fatigue the intensity of the stimulation will be increased. If fatigue does not occur prior to 30 minutes, the individual will advance to FES-rowing. If fatigue occurs prior to 30 minutes and at maximal intensity (approximately 100mA), the subject will engage in two weeks (3x/week) of strength training using this same protocol. Previous experience has indicated that this protocol is effective in enhancing muscle strength. Following two weeks of training, the strength and endurance capacity of the knee-extensor muscles will be evaluated and further training will be performed, if necessary, including the additional use of the QAA-9054 Total Power strength training machine. The QAA-9054 is a unique machine that provides the safety of accommodating resistance without the need of eccentric contractions. This type of resistance will not only allow the proper resistance to be safely placed on the knee extensors but also the knee flexors. Our past experience has shown that the knee flexors may lag behind the knee extensors and prevent continuous FES-rowing. The Strength training will continue until the subject is able to complete the knee flexion-extension protocol for 30 minutes without rest. This may take between 2 and 12 weeks depending on the subject's response to the FES-strength training. Subjects will also be encouraged to begin arms only rowing during the initial FES-strength training period. This will be done at the same visits as the FES-strength training sessions. Participants will be seated on the rowing machine with the rowing seat locked in a fixed position and will perform short intervals of rowing at a moderate intensity using only their arms. Intensity will be monitored by heart rate and rating of perceived exertion. Subjects will be allowed to take the FES-device home after they have completed the first two weeks of training and have shown adequate understanding of how to use the device properly. Subjects will perform strength training session at Spaulding Boston or Spaulding Cambridge as needed during home strength training. Subjects will also be given a logbook to track their usage.

## PARTNERS HUMAN RESEARCH COMMITTEE

### DETAILED PROTOCOL

#### FES-RT

Subjects will begin with short intervals of FES-RT interspersed with rest intervals and/or arms-only rowing intervals depending on fitness level and the response to the FES. A maximum FES-rowing test will be performed at baseline. This will be repeated after three months of training and training intensity will be adjusted to maintain the training stimulus at the same relative intensity. The goal is for each volunteer to achieve an exercise intensity of 75-85% maintained for a continuous 30 minutes performed three times each week. A maximum FES-rowing test will be performed at the end of the six months of FES-RT to determine increases in fitness. Measurements of force produced at the foot and handle during FES-row training sessions will also be used to monitor training and possibly improve rowing technique.

#### Strength Training during FES-RT

After the first two weeks of FES-leg strength training (it may take longer depending on the subject's response, see above) and when the subjects have demonstrated the ability to properly use the stimulation unit, the stimulation unit will be used at home to continue with leg strengthening on non FES-rowing days (~3 days/week, 30-60 minutes/session). This can be closely monitored since they will also be exercising 3 times per week at Spaulding Boston or Spaulding Cambridge.

#### **2) ARMS-ONLY-RT GROUP(Acute SCI only)**

The arms-only-RT group will commence exercise training upon enrollment. Training sessions will be 3 times per week for 26 weeks. To parallel the FES-RT, the initial training sessions will also consist of 6 sets of arms-only rowing for five minutes at 60% of VO2peak with a work-to-rest ratio of 2:1 and progress over the six months to an exercise intensity of 75-85% maintained for 30 minutes performed three times each week. The arms-only-RT group will also perform the FES-leg strength training protocol as described above during their six months of arms-only training. During this time they will not use the FES-device on the rowing ergometer. Strengthening the leg muscles during the arms-only period will lessen leg muscle atrophy and allow faster progress in FES-row training when they enter that phase of the study. A maximum arms-only rowing test will be performed at baseline. This will be repeated after three months of training and training intensity will be adjusted to maintain the training stimulus at the same relative intensity. A maximum arms-only rowing test will be performed at the end of the six months of training to determine increases in fitness. Subsequently, after the six months of arms-only-RT, subjects will begin the FES-RT as described above.

#### **3) WAIT-LIST GROUP(Acute SCI only)**

## PARTNERS HUMAN RESEARCH COMMITTEE

### DETAILED PROTOCOL

The wait list group will not participate in any row training for 6 months. A maximum arms-only rowing test will be performed immediately after enrollment, after initial familiarization with arms-only-RT equipment (usually 2-3 sessions) and will be repeated after 3 and 6 months (before FES-RT begins). The wait-list group will also perform the FES-leg strength training protocol as described above during the six months of the wait-list period. During this time they will not use the FES-device on the rowing ergometer. Strengthening the leg muscles during the wait-list period will lessen leg muscle atrophy and allow faster progress in FES-row training when they enter that phase of the study. At the end of the 6 month wait period, subjects will begin the FES-RT as described above.

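### Both comparator groups receive FES leg strengthening, so wait-list change is not plain expected decline; separately, the start of the FES-RT 3- and 6-month clock is not consistently defined

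*Combined protocol and SAP*

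**What the plan says.** **Comparators.** Section III gives each comparator a purpose. For the wait-list: "A six month time control will provide data on expected declines". Arms-only-RT is included because it "represents a form of arms-only exercise that would be available to those with SCI". The same section keeps all participants on usual rehabilitation but rules out outside exercise that duplicates a study intervention, with FES-cycling as its example. In Section II, Aim 1 concerns changes "resulting from FES-RT in comparison to a time (wait-list) control and to arms-only row training", and the Aim 2 hypothesis is that "FES-RT will prevent the worsening lipid profile and compromised baroreflex function occurring with acute SCI".

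Section V, 3) Wait-list group, says: "The wait-list group will also perform the FES-leg strength training protocol as described above during the six months of the wait-list period". The reason given is: "Strengthening the leg muscles during the wait-list period will lessen leg muscle atrophy and allow faster progress in FES-row training". Section V, 2) Arms-only-RT group, says: "The arms-only-RT group will also perform the FES-leg strength training protocol as described above during their six months of arms-only training". Neither Section II nor Section VI mentions this strengthening.

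**Timing in FES-RT.**
- FES-strength training prior to FES-RT: a participant who passes the 30-minute leg test goes straight to FES rowing. Otherwise a strengthening lead-in of 2 to 12 weeks comes first, during which arms-only rowing is encouraged.
- FES-RT: maximum tests are timed by three months of training and by the end of six months of FES-RT.
- Study Procedure Time Line: the FES maximum test, lab visit and DXA share one Baseline column and one 6-month column.
- Study Assessments: anyone needing more than eight weeks to reach the baseline FES maximum test has an extra assessment.
- Section VI: the Power analysis paragraph uses common 3- and 6-month indicators, and Primary data analysis tests outcomes six months after baseline.

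**The concern.** The hypotheses say that FES-RT will mitigate, prevent or counter changes that follow acute SCI. That reading needs a control group whose change shows what would otherwise happen. Here the controls receive a study-supplied FES leg intervention that the protocol itself expects to act on leg muscle. If wait-list change is published as the expected decline, it is mislabelled. If it is small, readers may conclude either that little decline occurs or that FES-RT adds nothing.

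The clock raises a second, independent issue. If FES-RT visits are counted from the start of rowing and comparator visits from enrolment, the same 6-month indicator stands for different elapsed times. The direction is uncertain: extra time allows more decline, which counts against FES-RT, while a full six months of rowing counts for it.

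**Working it through.** The plan states no figure on either issue to reproduce. The first is settled by comparing the text; the second is arithmetic on the plan's own durations.

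**1. What each group receives in the first six months**

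| Group | Rowing | FES leg strengthening |
|---|---|---|
| FES-RT | FES rowing; arms-only rowing encouraged in any lead-in | Lead-in if needed, then home sessions on days without FES rowing (about 3 days a week, 30–60 minutes) |
| Arms-only-RT | Arms-only, 26 weeks | Yes, by cross-reference |
| Wait-list | None | Yes, by cross-reference |

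The cross-reference in the two comparator sections has two possible targets:
- Only the protocol that precedes FES-RT. That protocol runs until the 30-minute criterion is met, so comparators could stop early while FES-RT participants continue at home. The backgrounds would then differ.
- Also the continuing home strengthening. The background would then be common to all three groups. But that section schedules sessions around FES-rowing days, which the comparators do not have.

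The text does not settle which applies. Under either, wait-list change is not change under usual rehabilitation alone. In addition, early enrollees may strengthen before any study assessment (the Notes that close the alternate training sites text).

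No effect of strengthening on visceral fat, HOMA, lipids, baroreflex gain, LV wall thickness or LV diastolic velocity is given, so no dilution or power loss can be computed.

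**2. The clock**

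Inputs: six months = 26 weeks (2) Arms-only-RT group); lead-in L = 2 to 12 weeks (FES-strength training prior to FES-RT); extra assessment after more than 8 weeks (Study Assessments). Assumptions: three months = 13 weeks, 26 weeks also applies to the wait-list, and the Baseline lab visit and DXA fall at the start of the lead-in.

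*Counted from the start of FES rowing*, time since Baseline:
- 6-month visit: 26 + L, so 26 + 2 = 28 to 26 + 12 = 38 weeks, against 26 (28/26 = 1.08; 38/26 = 1.46; that is, 8% to 46% longer).
- 3-month visit: 13 + 2 = 15 to 13 + 12 = 25 weeks, against 13.

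*Counted from Baseline*, weeks of FES rowing completed:
- 6-month visit: 26 − 12 = 14 to 26 − 2 = 24 (14/26 = 54%; 24/26 = 92%).
- 3-month visit: 13 − 12 = 1 to 13 − 2 = 11.

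Participants who pass the 30-minute test at once have L = 0 and are unaffected.

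*Does the extra assessment close the gap?* If the baseline FES maximum test follows the lead-in directly, a lead-in of up to 8 weeks triggers none, and on the rowing clock the 6-month visit is then up to 26 + 8 = 34 weeks after Baseline. Above 8 weeks it covers bloods and baroreflex testing, hence HOMA, lipids and baroreflex gain: 3 of the 6 outcomes named in Aims 1–3. It has no DXA, so visceral fat is not covered. It has no echocardiography either, though that is partly moot because the Echocardiography note ends those tests as of 1/1/19. Section VI does not say how the extra data enter the model.

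**The case against.** On strengthening, the strongest reply is that it is openly described, has a stated rationale and is given in all groups. A background treatment is legitimate, and randomisation protects the contrasts. All of that stands. Section III also never says that the time control is free of study intervention, and the only effect claimed for the strengthening is on leg muscle atrophy, which is not an Aim 1–3 outcome. So a reader might infer that the wait-list comparison is invalid or useless; the documents do not support that. Nor do they support saying that a null result could never count against FES-RT. Change within FES-RT is observed, and if both groups worsen, worsening was not prevented. The ambiguity is greatest when both groups stay flat.

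On the clock, the two readings are not equally likely. Section III speaks of six months of FES-RT, the maximum tests are timed by training, and the extra assessment makes most sense if follow-up runs from the baseline FES maximum test. This stands too: the text leans toward the rowing clock. But no sentence defines it, Primary data analysis is anchored to baseline, and the rowing clock is the one that makes elapsed time differ between groups.

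It would also be tempting to treat Baseline as always pre-training and as the date of the first scan. Neither holds for everyone: early enrollees may already have strengthened, and DXA Scan(s) allows a recent earlier scan to serve as baseline.

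**Conclusion.** Both parts hold in limited form, and both should be fixed.

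(1) Wait-list change is change under rehabilitation plus FES leg strengthening and should not be labelled expected decline. A null FES-RT versus wait-list result would not by itself show that FES-RT fails to mitigate decline. The randomised comparisons remain valid. The size and direction of any distortion are unknown, and no power loss should be quoted.

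(2) The FES-RT clock is not consistently defined. For participants who need a lead-in, the favoured rowing clock puts the 6-month visit 2 to 12 weeks later than in the comparators; the less favoured Baseline clock leaves 14 to 24 weeks of FES rowing. These ranges rest on the week conversions and on Baseline falling at the start of the lead-in. The number of participants affected is not given and may be small.

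**What to change.** **Strengthening.** Reconcile Sections II and III with the two comparator sections of Section V. State whether the cross-reference covers only the pre-rowing protocol or also the continuing home strengthening. Then describe FES-RT versus wait-list and FES-RT versus arms-only-RT with the leg strengthening actually given in each group, calling it a common background only if the continuing part also applies to the comparators. Do not label wait-list change as expected or natural decline. Report delivered strengthening by group from logbooks and session records, including any before Baseline.

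**Clock.** Reconcile the FES-strength training and FES-RT text with Study Assessments, the Time Line and Primary data analysis, and state which event starts the clock. Name one model baseline for all acute groups. The Time Line Baseline is the only scheduled FES-RT visit with DXA before the 6-month visit, though it is not pre-training for every early enrollee. State how the extra assessment is used, for example in a sensitivity analysis. Add an analysis using actual elapsed time from the date of each baseline measurement; for visceral fat use the actual scan date and state that change between the two scans is assumed linear. Report elapsed time and weeks of FES rowing by group at each visit.

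**Cost.** Mostly wording, one further analysis and summaries of exposure and visit dates. The stated question becomes narrower, and visceral fat carries a linearity assumption. Each clock has a price: from Baseline, the 6-month DXA may follow as little as 14 weeks of FES rowing, with no later scan listed for FES-RT; from the start of rowing, elapsed time exceeds the comparators' by 2 to 12 weeks. This point does not choose between them. Visits already made cannot be moved, and no change to anyone's training is proposed.
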